**Outcomes:**

1. Primary Endpoint:
  - a. Progression to require mechanical ventilation
2. Secondary Endpoints:
  - a. Day 28 all-cause mortality
  - b. Ventilator days
  - c. ICU days
  - d. Central catheter thrombotic events
  - e. Diagnosed VTE
3. Exploratory Endpoints:
  - a. Change in D-Dimer
  - b. Change in Ferritin
  - c. Change in CRP
  - d. Change in LDH
  - e. Change in Triglycerides

### **Adverse Events:**

Patients will be followed for 28 days during which time. All adverse events (AE) and serious adverse events (SAE) will be recorded including, but not limited to:

1. Minor Bleeding: Any sign or symptom of hemorrhage (i.e., more bleeding than would be expected for a clinical circumstance, including bleeding found by imaging alone) that does not fit the criteria for the definition of major bleeding but does meet at least one of the following criteria:
  - i. requiring medical intervention by a healthcare professional
  - ii. leading to hospitalization or increased level of care
  - iii. prompting a face to face (i.e., not just a telephone or electronic communication) evaluation (26)
2. Major bleeding: Bleeding in non-surgical patients is defined as having a symptomatic presentation and 1:
  - i. Fatal bleeding, and/or
  - ii. Bleeding in a critical area or organ, such as intracranial, intraspinal, intraocular, retroperitoneal, intra-articular or pericardial, or intramuscular with compartment syndrome, and/or
  - iii. Bleeding causing a fall in hemoglobin level of  $20 \text{ g L}^{-1}$  ( $1.24 \text{ mmol L}^{-1}$ ) or more, or leading to transfusion of two or more units of whole blood or red cells. (26)
3. Thrombocytopenia (Heparin induced)

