**Study Procedure:**

1. Patients admitted to HFH with suspected/identified COVID-19 infection will be reviewed daily
2. Those patients that fulfill the inclusion / exclusion criteria will be approached regarding participation in the study. If the patient is intubated, their designated representative will be approached regarding participation in the study.
3. If after answering all questions they agree to participate, an Informed Consent Form will be signed with a copy provided to the patient or their representative.
4. After enrollment, participants will be randomly assigned in a 2:1 ratio to the intervention or standard care control arm. Randomization will be stratified by stable/non-stable status and creatine clearance rate, using sequentially numbered, opaque, sealed envelope (SNOSE) technique for the allocation concealment.
5. Once enrolled, the primary patient history and laboratories will be reviewed, and data collected.
6. Orders for Enoxaparin or high intensity unfractionated heparin IV will be started within six hours of enrollment:
  - a. Options for stable patient (no procedures, hemodynamically stable):
    - i. CrCl  $\geq$  30 mL/min: Enoxaparin 1 mg/kg Q 12 hours
    - ii. CrCl of 15-29 mL/min: Enoxaparin 1 mg/kg Q 24 hours
    - iii. CrCl  $<$  15, rapidly fluctuating renal function, AKI/ESRD on IHD or CRRT: Heparin infusion at 12 units/kg/hr without initial bolus targeting aPTT 1.5-2.5 (55-75 seconds) normal range; dosing and monitoring per the HFH Low Intensity Heparin Protocol Guidelines. (21)
  - b. Options for unstable patient (anticipated procedures, hemodynamically unstable, severe critically illness):
    - i. Heparin infusion at 12 units/kg/hr without initial bolus targeting aPTT 1.5-2.5 (55-75 seconds) normal range
7. Duration of study anticoagulation:
  - a. No acute venous thromboembolism: anticoagulation throughout hospital stay and for six weeks post discharge.
  - b. New acute indication (DVT, PE, atrial fibrillation) for anticoagulation that develops during study treatment: 3 months; agent selection based on treatment team.
8. In the event of development of
  - a. Suspected or confirmed heparin induced thrombocytopenia without thrombosis (isolated HIT): (22-25)
    - i. Treat patient for 4 weeks with one of the following options given the clinical scenario:
      1. Options for stable patient (no procedures, hemodynamically stable):
        - a. CrCl  $\geq$  30 and weight  $>$  50 kg: Fondaparinux 2.5 mg SubQ Daily

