        - b. CrCl  $\geq$  30: Rivaroxaban 15 mg PO BID x 15 days, then 20 mg PO QD

- c. CrCl < 30: Apixaban 5 mg PO BID
  2. *Option for unstable patients (anticipated procedures, hemodynamically unstable, severe critically illness):*
    - a. Bivalirudin – goal PTT 1.5-2.5 times baseline PTT; dosing and monitoring per the HFHS HIT Guidelines. (Appendix A)
      - i. CrCl >60 mL/minute: 0.15 mg/kg/hr
      - ii. CrCl 30 to 60 mL/minute: 0.08 mg/kg/hr
      - iii. CrCl <30 mL/minute or dialysis: 0.05 mg/kg/hr
      - iv. CRRT: 0.07 mg/kg/hr
    - b. Suspected or confirmed heparin induced thrombocytopenia with thrombosis (HITT):
      - i. Treat patient for 3 months with one of the following options given the clinical scenario:
        1. *Stable patients (no procedures, hemodynamically stable):*
          - a. CrCl < 30: Apixaban 10 mg PO BID, then Apixaban 5 mg PO BID thereafter
          - b. CrCl ≥ 30: Fondaparinux
            - i. Weight < 50 kg: 5 mg SubQ Daily
            - ii. Weight 50-100 kg: 7.5 mg SubQ Daily
            - iii. Weight > 100 kg: 10 mg SubQ Daily
          - c. CrCl ≥ 30: Rivaroxaban 15 mg PO BID x 15 days, then 20 mg PO QD
        2. *Unstable patients (anticipated procedures, hemodynamically unstable, severe critically illness):*
          - a. Bivalirudin: goal PTT 1.5-2.5 times baseline PTT; dosing and monitoring per the HFHS HIT Guidelines
            - i. CrCl >60 mL/minute: 0.15 mg/kg/hr
            - ii. CrCl 30 to 60 mL/minute: 0.08 mg/kg/hr
            - iii. CrCl <30 mL/minute or dialysis: 0.05 mg/kg/hr
            - iv. CRRT: 0.07 mg/kg/hr
  9. The patients will be monitored after the initiation of therapy.
    - a. The first follow-up will be twelve hours after the start of anticoagulation.
    - b. Evaluation of clinical status will be completed twice daily to monitor progression of hypoxemia, respiratory failure, development of ARDS.
    - c. Daily laboratory testing including CBC with differential, electrolytes, PT, aPTT, INR, D-Dimer.
    - d. Ferritin, LDH, Triglycerides will be checked QOD as per Henry Ford Hospital COVID-19 Management guidelines.
  10. All patients who are in the control group will receive standard of care therapy inclusive of VTE prophylaxis and proning if part of routine care.

11. Post-discharge follow-up:
  - a. Patients will be maintained on anticoagulation upon discharge.
  - b. Patient contact 2 weeks post discharge
  - c. D-Dimer to be drawn at 4 weeks

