  - d. Patient contact 6 weeks post discharge
    - i. If D-Dimer remains elevated, discussion regarding continuation of anticoagulation vs. evaluation of VTE.

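### Adverse events are recorded for 28 days, but planned study anticoagulation runs through the hospital stay plus 42 days, so at least the last 14 treatment days have no assigned bleeding record

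*Protocol*

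**What the plan says.** The safety window is in the protocol's Adverse Events section: "Patients will be followed for 28 days during which time". The sentence stops there. The next one reads "All adverse events (AE) and serious adverse events (SAE) will be recorded including, but not limited to", followed by minor bleeding, major bleeding and heparin-induced thrombocytopenia. No starting point is given for the 28 days.

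The length of treatment is in Study Procedure. Step 7a gives "No acute venous thromboembolism: anticoagulation throughout hospital stay and for six weeks post discharge". Step 7b gives a longer course for some patients: "New acute indication (DVT, PE, atrial fibrillation) for anticoagulation that develops during study treatment: 3 months". Step 8b, on heparin-induced thrombocytopenia with thrombosis, has "Treat patient for 3 months with one of the following options given the clinical scenario". Step 11a confirms that treatment continues after the hospital stay: "Patients will be maintained on anticoagulation upon discharge".

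Step 11 also schedules a contact two weeks after discharge with no stated content, a D-dimer at four weeks, and "Patient contact 6 weeks post discharge". The only content given for that last contact concerns a D-dimer that is still raised: whether to continue anticoagulation or evaluate for VTE. Under step 10, controls receive standard care including VTE prophylaxis. No extended course is assigned to them.

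**The concern.** Bleeding is the main foreseeable harm of the strategy under test, and the exclusion criteria are built largely around it. The strategy has an in-hospital part and a six-week outpatient part. If recording of bleeding stops while the outpatient part is still running, the safety conclusion covers only part of what was tested.

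The uncovered weeks are also weeks in which the arms differ by design, because only the intervention arm is assigned an extended course. Diagnosed VTE, a secondary endpoint, carries no 28-day limit, and the 6-week contact mentions VTE. Benefit and harm could therefore be counted over different periods.

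A statistical analysis plan cannot repair this later. It can only analyse events that the protocol arranged to collect.

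**Working it through.** The protocol derives no figure for exposure or bleeding, so there is none to reproduce. Its sample size of 1031 does not enter the check.

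**Inputs**
- Safety window: 28 days, start not stated (Adverse Events).
- Planned course without VTE: hospital stay plus six weeks, that is L + 42 days (step 7a). L is the stay in days from enrolment. Orders start within six hours of enrolment (step 6), so enrolment is taken as treatment day 0.
- L is an assumption. The protocol gives no length of stay, so a range of 3 to 28 days is shown.

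**Formulas**
- Window starts at enrolment: uncovered days = (L + 42) − 28 = L + 14; share = (L + 14)/(L + 42).
- Window starts at discharge and in-hospital events are also recorded (the most generous reading): uncovered days = 42 − 28 = 14; share = 14/(L + 42).

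| Stay L | Planned course | Uncovered, from enrolment | Share | Uncovered, from discharge | Share |
|---|---|---|---|---|---|
| 3 | 45 | 17 | 38% | 14 | 31% |
| 5 | 47 | 19 | 40% | 14 | 30% |
| 10 | 52 | 24 | 46% | 14 | 27% |
| 20 | 62 | 34 | 55% | 14 | 23% |
| 28 | 70 | 42 | 60% | 14 | 20% |

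No length of stay closes the gap, since six weeks alone exceeds 28 days.

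**Do the contacts close it?** The 2-week contact falls on day L + 14 from enrolment, inside a 28-day window only if L is 14 or less. The 6-week contact falls on day L + 42 from enrolment, or day 42 from discharge, and so lies outside the window on either reading. Neither contact is assigned to collect bleeding or other adverse events.

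**From treatment time to bleeds.** Suppose the daily bleeding hazard in hospital is k times the hazard after discharge. With the window starting at enrolment, the uncovered share of expected bleeds is (L + 14)/(kL + 42):

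| k | L = 5 | L = 10 | L = 14 |
|---|---|---|---|
| 1 | 19/47 = 40% | 24/52 = 46% | 28/56 = 50% |
| 3 | 19/57 = 33% | 24/72 = 33% | 28/84 = 33% |
| 5 | 19/67 = 28% | 24/92 = 26% | 28/112 = 25% |
| 10 | 19/92 = 21% | 24/142 = 17% | 28/182 = 15% |

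The values of k are illustrative; the protocol gives no hazard.

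**The case against.** The strongest reply is that the aim is to prevent respiratory failure, the primary endpoint is mechanical ventilation, and mortality is set at day 28. A 28-day bleeding window applied equally to both arms matches that horizon and gives a valid comparison. This stands. It lowers the severity, but it does not supply safety data for the rest of the course.

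A second reply is that the broken sentence leaves the recording of adverse events with no time limit. That is possible, though a 28-day cap is the likelier intent. Even so, no post-discharge procedure is assigned to find the events.

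A reader might also infer more than the documents support:
- **That a large part of the bleeding risk is never measured.** The figures are shares of planned treatment time. If hazard is concentrated in hospital, the share of bleeds is smaller, and patients who die in hospital have no post-discharge exposure. A 6-week contact also exists at which bleeding could be asked about.
- **That heparin-induced thrombocytopenia would be understated.** Steps 7a and 11a do not name the agent used after discharge, so continued heparin exposure is not shown.
- **That the contacts ignore VTE.** Step 11d mentions evaluation of VTE when D-dimer stays raised. The gap concerns bleeding and other adverse events.
- **That unobserved exposure has a known ceiling.** With all 687 intervention patients discharged alive, 14, 24 or 34 uncovered days each give 687 × 14/365 = 26, 687 × 24/365 = 45 or 687 × 34/365 = 64 patient-years. The result moves with the assumed stay.
- **That the three-month courses enlarge the gap in the randomized comparison.** They treat events arising during the study, and under step 7b the treatment team selects the agent. They are weak support, and the point does not need them.

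**Conclusion.** The Adverse Events section and Study Procedure steps 7 and 11 do not fit together. The period for recording harm is shorter than the planned course for every length of stay and on either reading of when it starts. At least 14 planned treatment days are uncovered. If the window starts at enrolment, the shortfall is 40–55% of treatment time for assumed discharge between day 5 and day 20.

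This rests on the planned course being followed, on survival to discharge, and on an assumed length of stay. The share of bleeds missed cannot be derived from the protocol.

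The consequence is limited but real: bleeding over the full tested course would be incompletely measured in a period when the arms differ by design. The 28-day bleeding comparison and the primary endpoint are not affected. This should be fixed, but it does not undermine the trial's main result.

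**What to change.** Reconcile the Adverse Events section with Study Procedure steps 7 and 11. No view is taken here on how long treatment should last.

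1. State that the adverse-event window starts at randomization, and repair the broken sentence.
2. Record bleeding, VTE, serious adverse events and death in both arms through the 6-week post-discharge contact. Use the 2- and 6-week contacts already scheduled, and state that they apply to both arms.
3. Compare bleeding between arms over one common horizon counted from randomization and long enough to cover the planned course. For example, 28 + 42 = 70 days would cover stays of up to 28 days. Use time-to-event methods with censoring. Follow-up should not depend on how long a patient stays on drug, because longer observation of the treated arm could by itself produce a difference in crude bleeding proportions.
4. Keep day 28 for mortality and as a reported cut for bleeding.

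One limit remains. A patient discharged early is last contacted on day L + 42, before a longer horizon is reached. Censoring then depends on the discharge date, which treatment might affect. Follow-up to day 42 is complete for every survivor who is reached, so a bleeding estimate at that day is a useful check.

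The cost is a few added questions per contact and one amendment. If step 11 was meant for the intervention arm only, add two calls for each of up to 344 controls, at most 688 calls. Sample size and treatment do not change.

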### **Data Collection:**

1. Baseline characteristics:
  - a. Demographics: Age (years), Gender, Height, Weight, Race/Ethnicity
  - b. Comorbidities
  - c. Preadmission Medications
2. Laboratory evaluation:
  - a. CBC, PT, aPTT, INR, D-Dimer, electrolytes, creatinine clearance, LDH, ferritin, triglycerides, high sensitivity troponin, fibrinogen, anti-thrombin III activity, SOFA score
3. Clinical evaluation (twice daily measurements)
  - a. Patients not intubated
    - i. COVID-19 therapy (azithromycin, hydroxychloroquine, solumedrol, etc.)
    - ii. Modified Borg score with visual analog
    - iii. Amount of supplemental oxygen
    - iv. Oxygen saturations
    - v. Notation of awake prone positioning

- vi. Previous clotting event of central venous access or peripheral arterial access
- b. Ventilated Patients
  - i. COVID-19 therapy (azithromycin, hydroxychloroquine, solumedrol, etc.)
  - ii. FiO2
  - iii. PEEP
  - iv. SaO2
  - v. P/F Ratio
  - vi. Static lung compliance
  - vii. Notation of prone positioning
  - viii. Volume status
  - ix. SOFA score
  - x. Previous clotting event of central venous access or peripheral arterial access
- 4. Radiographic imaging
  - a. CT or chest radiograph reports will be collected and temporally related to point of admission to study. Subsequent imaging will be based on clinical requirements.

**ISHT SIC Score**

Variable	Value	Points
Platelets, K/ $\mu$ L	>100	0
	50-100	1
	<50	2
INR	<1.3	0
	1.3-1.7	1
	>1.7	2
D-Dimer, ng/mL	<400	0
	400-4000	2
	>4000	3
Fibrinogen, mg/dL	>100	0
	<100	1

**Data Analysis:**

All statistical analyses will be conducted according to the intention-to-treat principle. Thus, patients will be analyzed according to the arm to which they were allocated.

Data will be summarized by intervention arms using bivariate analyses. All hypothesis testing will be carried out at the 5% (2-sided) significance level unless otherwise specified. We will report the number and percentage of primary outcome. To assess the intervention effect, logistic regression models, generalized linear models, Kaplan Meier plots and Cox proportional hazard models will be performed for both primary and secondary outcomes, as appropriate.

Descriptive analyses will be performed for the exploratory outcomes.

An interim safety analysis is will be performed upon recruitment of patient 329.

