**Justification for Number of Subjects or Data:**

Sample size estimate suggest that 1031 participants are required.

The primary outcome measure for the power calculation is the difference of intubation rate between intervention arm (systemic anticoagulation using enoxaparin subcutaneous (or unfractionated heparin) and control arm (current standard care). We expect the intervention arm will provide a reduction by 30%. The baseline intubation rate was estimated 25 % in the control arm. Assuming alpha at two-sided 0.05 and power at 80% indicates that a total sample size of 1031participants (687 in the intervention and 344 in the control arm) would be required.

Required sample sizes	
Assuming 80% power, alpha=0.05 and two-sided testing	
Reduced by	Estimated intubation rate in COVID-19 inpatients with standard care
10%	10181 (6787:3394)
20%	2435 (1623:812)
30%	1031 (687:344)
40%	548 (365:183)
50%	329 (219:110)

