## **Randomization**

Participants will be randomly assigned in a 2:1 ratio to the intervention or standard care control arm. Randomization will be stratified by stable/non-stable status and creatinine clearance rate. The allocation sequence will be generated using random permuted blocks within stratum. Using restricted randomization within the stratum ensures that number of participants is balanced between study arms within stratum and the stratification factors will be balanced in each study arm.

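### The Data Analysis section names no single primary test for intubation and does not carry the two randomisation strata into the analysis

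*Protocol*

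**What the plan says.** On the design side, the Randomization section states: "Randomization will be stratified by stable/non-stable status and creatinine clearance rate". Allocation is 2:1, in permuted blocks within stratum. Study Procedure, item 4, repeats the stratification, and item 6 describes unstable patients as those with anticipated procedures, haemodynamic instability or severe critical illness.

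On the analysis side, the Data Analysis section opens with intention-to-treat and then says: "Data will be summarized by intervention arms using bivariate analyses". It sets the level: "All hypothesis testing will be carried out at the 5% (2-sided) significance level unless otherwise specified". The number and percentage with the primary outcome are to be reported. For comparing the arms, the plan is that "logistic regression models, generalized linear models, Kaplan Meier plots and Cox proportional hazard models will be performed for both primary and secondary outcomes"; the sentence closes with a qualifier that the methods apply as fits the case. No method is called primary, and neither the strata nor any other covariate is mentioned.

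The sample size section takes the difference in intubation rate as its outcome measure: "The baseline intubation rate was estimated 25 % in the control arm", "We expect the intervention arm will provide a reduction by 30" per cent, "Assuming alpha at two-sided 0.05 and power at 80" per cent, giving "687 in the intervention and 344 in the control arm". The primary endpoint under Outcomes is progression to mechanical ventilation, with no time point.

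**The concern.** Two things are left unconnected.

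First, one sentence offers both binary models and time-to-event models for the primary outcome. They estimate different quantities: an odds ratio or a risk difference in one case, a hazard ratio in the other. Because the endpoint has no time point, either family fits it. The stated 5% level is therefore not tied to one test, and in an open-label trial it is worth fixing that test before results are seen.

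Second, the design balances the arms on two factors, at least one of which (stability) is plausibly prognostic for intubation. After stratified randomisation, an arm comparison that leaves out prognostic strata uses too large a standard error. It is conservative and gives up efficiency that the design makes available.

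**Working it through.** **Step 1. Reproduce 1031.** Inputs from the sample size section: control risk p0 = 0.25; 30% relative reduction, so p1 = 0.175; two-sided alpha 0.05; power 80%; ratio 2:1. For a pooled two-proportion test without continuity correction, the control-arm size is

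n0 = [1.96·√(1.5·p̄(1−p̄)) + 0.8416·√(p0(1−p0) + p1(1−p1)/2)]² / (p0−p1)²

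- p̄ = (0.25 + 2×0.175)/3 = 0.20
- First term: 1.96×√0.24 = 0.960
- Second term: 0.8416×√0.2597 = 0.429
- n0 = 1.389²/0.005625 ≈ 343.0, and 2·n0 ≈ 686.05

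Rounding each arm up gives 344 + 687 = 1031. Power at 344:687 is 80.1%. The calculation contains no strata, so 80% is what an unadjusted binary test delivers.

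**Step 2. True alpha when strata are left out.** With allocation balanced within strata, the difference in proportions varies according to V_W = Σ w·p(1−p), taken within strata. The unadjusted test uses V_T = p(1−p) at the overall risk. With k = √(V_W/V_T), true alpha = 2[1 − Φ(1.96/k)].

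The documents give no stratum sizes or risks. Assume a 70/30 stable/unstable split with an overall risk of about 25%:

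| Assumed risk, stable / unstable | V_W | V_W/V_T | 1.96/k | True alpha |
|---|---|---|---|---|
| 22% / 32% (mild) | 0.7×0.1716 + 0.3×0.2176 = 0.1854 | 0.989 | 1.971 | 4.9% |
| 16% / 46% (moderate) | 0.7×0.1344 + 0.3×0.2484 = 0.1686 | 0.899 | 2.067 | 3.9% |
| 12% / 55% (strong) | 0.7×0.1056 + 0.3×0.2475 = 0.1482 | 0.792 | 2.202 | 2.8% |

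Simulation of mild, moderate and strong effects with a 70/30 split gives 4.9%, 3.9% and 2.7%.

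**Step 3. Power at 344:687.** This was simulated with a relative risk of 0.7 in every stratum, comparing the unadjusted pooled z-test with a stratified Cochran-Mantel-Haenszel (CMH) test. For the 70/30 split, the gain from stratifying is about 0.3, 2.1 and 4.3 points. For four assumed strata (60/15/15/10%):

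| Assumed control risks | Unadjusted power | CMH power | Gain (points) | Unadjusted true alpha |
|---|---|---|---|---|
| All 25% | 79.9% | 79.9% | 0 | 5.0% |
| 20% to 46% | 80.5% | 81.3% | 0.8 | 4.8% |
| 16% to 57% | 81.3% | 83.6% | 2.3 | 4.0% |
| 10% to 76% | 83.1% | 88.4% | 5.3 | 2.2% |

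CMH stays at about 5% error throughout. Unadjusted power stays at or above about 80% in every row.

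**Step 4. Free choice of test.** Suppose either a binary test or a Cox/log-rank test at 5% could count as success. The error is then 1 − P(|Z1| < 1.96 and |Z2| < 1.96) for correlated normal statistics:

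- correlation 0.99: 5.7%
- correlation 0.97 (the value simulated): 6.2%
- correlation 0.90: 7.0%

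The conservatism of step 2 works the other way. With the moderate four-stratum risks, taking the better of the unadjusted binary and log-rank tests gave 5.2%.

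**The case against.** The strongest reply is that the section is silent on covariates rather than opposed to them. Logistic, generalized linear and Cox models can all carry the strata. The bivariate analyses are described as a way to summarise data by arm, not as the effect test. Covariate lists are commonly left to a statistical analysis plan, which may exist but is not shown. The closing qualifier can also be read as matching each model to its endpoint type, since the endpoints include counts of days as well as events. Logistic regression is itself a generalized linear model, so the real choice is binary against time-to-event. Reporting percentages and powering on rates both point to the binary side.

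Most of this stands, and it rules out three stronger readings that a reader might infer:

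- **That the models are unadjusted, or that the plan rejects the strata.** The text says neither.
- **That the trial loses planned power.** Step 1 shows that it does not; only an extra gain is forgone.
- **That the 5% claim is undefined or badly inflated.** Level and sidedness are stated, and the excess from a free choice is about 1 to 2 points before conservatism.

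What the reply does not remove is that the section goes beyond deferring detail. It assigns both families of model to the primary outcome, ranks none, and never links them to the rate difference used for sample size or to the strata used for randomisation.

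**Conclusion.** The point holds as a worthwhile, inexpensive clarification, not as a flaw that threatens the trial. The absence of a named primary test and the missing link to the sample size measure can be read directly from the protocol. The strata half rests on silence, so it is a recommendation to state something rather than evidence of a wrong analysis.

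The sizes depend on assumed stratum risks. If the strata do not predict intubation, nothing is lost by omitting them. If they do, the omission makes the test conservative (about 4.9%, 3.9% and 2.7% with a 70/30 split; as low as 2.2% in the widest four-stratum case) and forgoes up to about 5 points of power. The two effects pull in opposite directions on the error rate: omitting strata lowers it, while choosing freely between tests raises it to about 6% to 7% at correlations of 0.97 to 0.90.

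**What to change.** In Data Analysis, name one primary analysis: a comparison of intubation proportions adjusted for stability and creatinine clearance as randomised. Either of these would serve:

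- logistic regression on arm and strata, reported as a standardised risk difference with 95% CI, which matches the sample size measure; or
- a stratified Cochran-Mantel-Haenszel test.

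Apply the two-sided 5% level to that test only. Label Kaplan-Meier and Cox analyses, with the same strata, as supportive.

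The sponsor must also state the time point for the primary endpoint. Day 28 is attached in the protocol to mortality and to adverse-event follow-up, not to intubation, so it should not be assumed.

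The cost is a few lines of text. The strata are known for every patient at randomisation, so no new data are needed. The small downside is that some creatinine-clearance strata may be sparse. The stratification categories, which the Randomization section does not give, should be listed, with a merging rule fixed before the data are analysed.
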